**Anticipated Outcomes:**

*Primary Outcome:*

Assess relationship between trust in healthcare system and engagement in screening mammography program in local Hispanic women.

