Do trust in the healthcare system and/or health literacy impact engagement in a screening mammography program in the local Hispanic population? *We hypothesize that higher levels of trust and health literacy are positively related to engagement in a screening mammography program.*

Does a PN improve Hispanic women’s measures of trust in the healthcare system and satisfaction with communication in the screening mammography setting when compared to those receiving standard of care? *We hypothesize that women with access to a PN will have higher levels of trust in the healthcare system and satisfaction with communication than women receiving the standard of care.*

Methods:

*Study Design:* The study design is a randomized control trial. In this pilot study, 100 participants will be randomized to either a) the intervention, in which they receive care from the PN or b) the control, in which they receive the standard of care.

*PN Identification and Education:*

A PN will be identified and trained by [name], VICC Community Health Educator. [name] will supplement educational materials.

*Inclusion/Exclusion Criteria:*

Inclusion criteria will be Hispanic women meeting United States Preventive Services (USPSTF) criteria for screening mammography and criteria for clinical service coverage through the TN Breast and Cervical Cancer Screening Program.

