**Exclusion Criteria:**

- Personal history of breast cancer
- Current breast symptoms (palpable mass)

*Recruitment:*

We aim to recruit 100 women total. All participants will be informed that well woman screening is free under the TN Breast and Cervical Cancer Screening Program. Participants will be offered \$40 gift cards for compensation for participation. Two recruitment methods will be used.:

[figure not shown]
1. The research team will identify and recruit women meeting inclusion criteria from the MWCHC electronic medical record. Eligible participants identified from the MWCHC will be contacted via telephone. **[See recruitment material]**.
2. The research team will identify and recruit women from the local Hispanic community through churches, community organizations, and community events. We will also use radio announcements and Facebook for recruitment **[See recruitment material]**.

At the time of recruitment, women will be assisted in scheduling an appointment at MWCHC for well woman screening during a “Hispanic Clinic Day”.

*Hispanic Clinic Days:*

Women will be scheduled during one of five dedicated “Hispanic Clinic Days”. Each clinic day will host up to 20 women, to a target 100 participants. Each day there will be a morning session for 10 women and an afternoon session for 10 women. The bilingual research assistant and bilingual PN will be present during the Hispanic Clinic Days. At the start of each session, consent will be obtained from all potential participants, followed by baseline assessments, randomization and clinical care. Gift cards will be distributed at time of written consent.

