**HISPANIC CLINIC DAY FLOW CHART**

*Consent:*

Written informed consent will be obtained for all participants by the research assistant in person at MWCHC [**see attached consent**].

*Baseline Assessment:*

Immediately following consent, all participants will complete a baseline assessment (English or Spanish according to participant preference) to collect demographic information, trust in healthcare system assessment, and health literacy assessment [**see baseline survey**]. This assessment will be collected by paper and pencil with the help of the research assistant.

*Randomization:*

Women will be randomized to the control arm, the intervention arm 1 (individual education), or the intervention arm 2 (group education) immediately following consent. Randomization will be performed using the random number generator software available in the R statistical package ([www.r-project.org](http://www.r-project.org)).

*Control Arm:*

Immediately following consent and completion of the baseline assessment, women in the control arm will receive standard of care well woman screening. The control arm will receive screening results per MWCHC protocol.

*Intervention Arm 1:*

Immediately following consent and completion of the baseline assessment, women in the intervention arm 1 will participate in a 20-30 minute educational session [**see educational slides**] alone with the PN. Well woman screening will follow the educational session. The PN will be available to assist with questions and language interpretation as necessary. After standard delivery of screening results, the PN will contact these participants to answer any questions about their screening results and to assist with scheduling any additional tests necessary.

*Intervention Arm 2:*

Immediately following consent and completion of the baseline assessment, women in the intervention arm will participate in a 20-30 minute group educational session [**see educational slides**] from the PN. Well woman screening will follow the educational session. The PN will be available to assist with questions and language interpretation as necessary. After standard delivery of screening results, the PN will contact these participants to answer any questions about their screening results and to assist with scheduling any additional tests necessary.

*Post Assessment 2-5 Days After Delivery of Results:*

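### The primary outcome rests on an undefined 'engagement' with no planned analysis and, because trust is scored only in attenders, cannot speak for local Hispanic women generally; the randomised trust effect has no rank

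*Combined protocol and SAP*

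**What the plan says.** Under Anticipated Outcomes, the primary outcome reads "Assess relationship between trust in healthcare system and engagement in screening mammography program in local Hispanic women". It matches Objective 1. Objective 2 asks the same of health literacy. The only secondary outcome is the navigator's effect on satisfaction with communication (Objective 4).

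On timing, Recruitment states "At the time of recruitment, women will be assisted in scheduling an appointment at MWCHC for well woman screening". Hispanic Clinic Days then states "At the start of each session, consent will be obtained from all potential participants, followed by baseline assessments, randomization and clinical care". Baseline Assessment places the trust and literacy scales at that visit: "Immediately following consent, all participants will complete a baseline assessment". Besides the clinic's own records, the source population is the wider community: "The research team will identify and recruit women from the local Hispanic community through churches, community organizations, and community events".

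Objective 3 concerns the navigator's effect on trust, and Research Questions/Hypotheses makes it explicit: "We hypothesize that women with access to a PN will have higher levels of trust in the healthcare system and satisfaction with communication". The Healthcare System Distrust Scale is given at baseline and repeated at the post assessment (Item Development).

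Statistical Considerations lists descriptive statistics, a baseline-to-post comparison of knowledge, and a generic post-assessment comparison of intervention with control. Sample Size gives 50 per group for a success rate of 40% v 69%. Study Design has two groups ("100 participants will be randomized to either a) the intervention, in which they receive care from the PN or b) the control"), whereas Randomization describes a control arm and two education arms.

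**The concern.** An analyst who followed Statistical Considerations to the letter would never produce the primary result. To produce it, someone would have to choose a measure of engagement, a time point and a model, possibly after seeing the data. Two careful analysts could report different primary findings from the same trial.

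The population is a second difficulty. The outcome is worded for local Hispanic women, but every woman with a trust score has already booked, attended and consented. Women whose distrust kept them away are missing by design, and recruiting more women in the same way would not bring them in.

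Third, the comparison that randomisation supports, trust with a navigator against trust without one, carries no stated priority. A reader of the results could not tell whether it is a main finding or one of several post-assessment comparisons.

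**Working it through.** **Step 1: candidate meanings of engagement.** The plan applies the term to none of these.

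| Reading | Source | Consequence |
|---|---|---|
| Initial attendance | Hispanic Clinic Days | Constant among scored women; not estimable |
| Completing the index mammogram | Clinic-day care | Estimable only if some consenting women do not complete it |
| Return for diagnostics at 2-4 weeks | Delayed Chart Review | Only women who need follow-up |
| Intent to follow up | Post Assessment | Stated, not observed |
| Rescreening at 2-3 years | Delayed Chart Review; Timeline | Observable, but the review is worded as optional |

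The list may not be complete. Earlier screening history, for instance, could vary among attenders and precedes randomisation. All but the first reading can be studied, though only among attenders.

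**Step 2: the plan's own figure.** Inputs from Sample Size: 50 per group, 40% v 69%, two-sided 5%, continuity-corrected chi-squared test. The pooled rate is (0.40 + 0.69)/2 = 0.545. The null SE is sqrt(0.545 x 0.455 x 2/50) = 0.0996 and the alternative SE is sqrt(0.40 x 0.60/50 + 0.69 x 0.31/50) = 0.0953. Then z = (0.29 - 0.02 - 1.96 x 0.0996)/0.0953 = 0.785, a power of 78.4%. Exact enumeration of the corrected test gives 80.03%. The stated figure of at least 80% therefore reproduces within tolerance. The arithmetic is sound, but it sizes a comparison of two proportions, not an association between trust and engagement. With three equal arms and the education arms pooled (33 v 67), the exact power is 74.2%.

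**Step 3: detectable differences in trust.** The documents give no SD and no engagement rate, so results are in SD units with assumed rates. For a two-sample t test with 80% power and two-sided 5%, d = L x sqrt(1/n1 + 1/n2). L is the noncentrality giving 80% power: about 2.83 with 100 women and 2.836 with 80. Baseline adjustment multiplies d by sqrt(1 - r^2), which is 0.866 at an assumed r = 0.5.

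*Randomised trust contrast (80 assessed is an assumed loss):*

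| Groups | Unadjusted | Adjusted |
|---|---|---|
| 50 v 50 | 2.83 x 0.200 = 0.57 | 0.49 |
| 33 v 67 | 2.83 x 0.213 = 0.60 | 0.52 |
| 40 v 40 | 2.836 x 0.224 = 0.63 | 0.55 |
| 27 v 53 | 2.836 x 0.236 = 0.67 | 0.58 |

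*Engagement as rescreening (rates and loss assumed):*

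| Rescreened | 100 charts | 80 charts |
|---|---|---|
| 50% | 0.57 | 0.63 |
| 70% | 0.62 | 0.69 |
| 80% | 0.71 | 0.79 |
| 90% | 0.94 | 1.06 |

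*Other readings.* Index mammogram in 100 women: 0.94 SD at an assumed 90% completion and 1.30 SD at 95%. Return for diagnostics, if 10 to 20 women need it and 50% to 80% return (all assumed): 1.25 to 2.21 SD by normal approximation.

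At 50% rescreened the unadjusted figures equal those of the randomised 50 v 50 contrast. As the rate moves towards 90% the association loses precision, and baseline adjustment is a gain for the randomised contrast.

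**The case against.** The best defence is that engagement may be meant as engagement within the programme, so that initial uptake, a word the documents do not use, was never the target. In that case the attenders-only point is a limit on generalisation, and a defined association among attenders could properly stay primary in a pilot. This largely stands. A reader might infer that the primary outcome is impossible to estimate. The documents do not support that: it is true only if engagement means initial attendance. It is also fair that a plan which demoted the association without naming a replacement would have no primary outcome at all.

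A reader might also infer that Objective 3 has no analysis. That goes too far. Trust is repeated at the post assessment, and the generic between-group tests could cover it. A t test between randomised arms is valid, and baseline adjustment is a gain in efficiency. What Objective 3 lacks is rank.

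The baseline survey and post assessment are cited as attachments but were not available here. They may contain items on screening history or knowledge. They do not remove the gap, because the protocol's account of their contents calls nothing engagement and Statistical Considerations relates nothing to it. That the Timeline shows months 24-36 while Delayed Chart Review says the review may occur is not a contradiction, since a timeline can show the window for an optional activity. It matters only if rescreening becomes the chosen measure.

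Pilot status does not answer the main point: the plan claims formal 80% power and names a primary outcome, so that outcome has to be identifiable.

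**Conclusion.** The concern holds and must be fixed in two respects: the primary outcome is undefined and unanalysed, and its stated population is wider than the women who can be scored. The missing rank for Objective 3 should be settled in the same change, because it bears on which outcome is primary.

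The primary defect rests on the text and needs no assumed number. The detectable differences show only what each choice could resolve: 0.49 to 0.67 SD for the randomised contrast and 0.57 to 1.06 SD for rescreening. These depend on the assumed loss, correlation and rescreening rates. They do not show the stated power to be wrong for the comparison it describes, and the case for the randomised outcome rests mainly on definition, scope and randomisation.

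The absence of a named scale for trust in the provider, the knowledge wording and clustering by group session are separate, lesser points.

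**What to change.** 1. Name one primary outcome, so that the plan is never without one.
   - *Preferred:* the post-assessment Healthcare System Distrust score, navigator versus control, by linear regression adjusted for the baseline score. Satisfaction with communication stays secondary. This uses data the plan already collects. The cost is that the trust-engagement association loses primary rank.
   - *Alternative:* keep the association as primary, with engagement defined by one named measure and time point, and list the baseline-adjusted distrust comparison as a named secondary outcome.
2. In either case, restrict Objectives 1 and 2 and the wording of the association to women who attended. Analyse engagement by logistic regression on baseline distrust and literacy, adjusted for arm if the measure follows randomisation. If rescreening is chosen, commit to the 2-3 year chart review and state that clinic charts may miss screening done elsewhere. That commitment is a real cost, since the review is currently optional.
3. Reconcile two groups of 50 with the three arms under Randomization, say whether the education arms are pooled, and restate the sample-size sentence for the chosen primary, allowing for loss to the post assessment or chart review.

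The preferred option needs a protocol amendment but no new instrument or visit.

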**Secondary Outcome:**

Assessment of PN impact on Hispanic women’s measures of satisfaction with communication when compared to those receiving standard of care treatment in the screening mammography setting.

**Timeline:**

Month	
1-2	Identify and Educate Promotora Navigator, Identify and Educate Research Assistant
3-6	Recruitment Host Hispanic Clinic Days Collect Data
7-8	Delayed chart review for Return for Necessary Follow-Up Data analysis
24-36	Delayed chart review for follow-up screening

